9.5.1.5.2 SERIOUS ADVERSE EVENTS AND EVENTS ASSOCIATED WITH SPECIAL SITUATIONS

An SAE is any untoward medical occurrence that at any dose:

- Results in death
- Is life-threatening (ie, the subject was at immediate risk of death from the AE as it occurred; this does not include an event that, had it occurred in a more severe form or was allowed to continue, might have caused death)
- Requires inpatient hospitalization or prolongation of existing hospitalization
- Results in persistent or significant disability/incapacity
- Is a congenital anomaly/birth defect (in the child of a subject who was exposed to the study drug)

Other important medical events that may not be immediately life-threatening or result in death or hospitalization but, when based on appropriate medical judgment, may jeopardize the subject or may require intervention to prevent one of the outcomes in the definition of SAE listed above should also be considered SAEs. Medical and scientific judgment should be exercised in deciding whether expedited reporting is appropriate in such situations.

For this study, the following events should always be considered serious and reported as an important medical event if it does not meet other serious criteria:

- Serotonin syndrome (must have at least 1 of the following: Spontaneous clonus; Inducible clonus plus agitation or diaphoresis; Ocular clonus plus agitation or diaphoresis; Tremor plus hyperreflexia; Hypertonia plus temperature above 38°C plus ocular clonus or inducible clonus)
- Psychosis
- Suicidal behavior

- Priapism
- New onset valvular heart disease
- New onset pulmonary hypertension
- Malignant neoplasms, with the exception of basal cell and squamous cell carcinomas of the skin
- Fibroadenomas of the breast or ductal carcinoma in situ

The following additional study specific AE of interest should be reported using the procedures detailed in Reporting of SAEs (Section 9.5.4.1), even if the study specific event does not meet serious criteria. If the event meets seriousness criteria, it should be reported as an SAE as above. However, if the event listed below does not meet serious criteria, it should be noted as nonserious on the Adverse Event CRF:

- Suicidal ideation
- Euphoria

In addition to the above, events associated with special situations include pregnancy or exposure to study drug through breastfeeding; AEs associated with study drug overdose, misuse, abuse, or medication error. These events associated with special situations are to be captured using the SAE procedures but are to be considered as SAEs only if they meet 1 of the above criteria. All AEs associated with special situations are to be reported on the CRF whether or not they meet the criteria for SAEs.

All SAEs must be followed to resolution or, if resolution is unlikely, to stabilization.

The following hospitalizations are not considered to be SAEs because there is no “AE” (ie, there is no untoward medical occurrence) associated with the hospitalization:

- Hospitalizations for respite care
- Planned hospitalizations required by the protocol
- Hospitalization planned before informed consent (where the condition requiring the hospitalization has not changed after study drug administration)
- Hospitalization for administration of study drug or insertion of access for administration of study drug
- Hospitalization for routine maintenance of a device (eg, battery replacement) that was in place before study entry

9.5.1.5.3 LABORATORY MEASUREMENTS

Clinical laboratory tests to be performed, including hematology, chemistry, and urinalysis, are summarized in [Table 1](#). Subjects should be in a seated or supine position during blood collection. The Schedule of Procedures/Assessments ([Table 2](#)) shows the visits and time

points at which blood for clinical laboratory tests and urine for urinalysis will be collected in the study.

Table 1 Clinical Laboratory Tests

Category	Parameters
Hematology	Hematocrit, hemoglobin, platelets, RBC count, and WBC count with differential (bands, basophils, eosinophils, lymphocytes, monocytes, neutrophils)
Chemistry	
Electrolytes	Chloride, potassium, sodium
Liver function tests	Alanine aminotransferase, alkaline phosphatase, aspartate aminotransferase, gamma glutamyl transpeptidase, direct bilirubin, total bilirubin
Renal function tests	Blood urea/blood urea nitrogen, creatinine
Thyroid function	T4, TSH
Adrenal function	Cortisol
Sex hormones	Testosterone (male subjects), estradiol (female subjects),
Bone health assessments	Serum OC and PICP, Hydroxy-proline; Urine NTX
Prolactin	Fasting prolactin levels
Other	Albumin, calcium, globulin, glucose, HbA _{1c} , HDL cholesterol, lactate dehydrogenase, LDL cholesterol, phosphorus, total protein, total cholesterol, triglycerides, prolactin, uric acid, urine β -hCG
Urinalysis	Bacteria, casts, crystals, epithelial cells, glucose, ketones, occult blood, pH, protein, RBCs, specific gravity, WBCs

β -hCG = beta-human chorionic gonadotropin, HbA_{1c} = hemoglobin A_{1c}, HDL = high density lipoprotein, LDL = low density lipoprotein, OC = osteocalcin; NTX = N-telopeptide, PICP = carboxyterminal propeptide of type I procollagen; RBC = red blood cell, T4 = thyroxine, TSH = thyroid stimulating hormone, WBC = white blood cell.

Clinical laboratory tests during the study will be performed by a central laboratory. All blood and urine samples will be collected and sent to the central laboratory on the day of collection unless otherwise instructed. In cases of a safety concern, blood samples will be split (or 2 samples drawn) to allow a local laboratory analysis in addition to the central laboratory.

A laboratory abnormality may meet the criteria to qualify as an AE as described in this protocol (see [Section 9.5.1.5.1](#)) and the CRF Completion Guidelines. In these instances, the AE corresponding to the laboratory abnormality will be recorded on the Adverse Event CRF.

9.5.1.5.4 VITAL SIGNS AND WEIGHT MEASUREMENTS

Vital sign measurements (ie, systolic and diastolic BP [mmHg], pulse [beats per minute], respiratory rate [per minute], body temperature [in centigrade]), and weight (kg) will be obtained as designated in the Schedule of Procedures/Assessments (Table 2) by a validated method. BP and pulse will be measured after the subject has been sitting for 5 minutes. All BP measurements should be performed on the same arm, preferably by the same person.

When vital signs are to be obtained concurrently with PK or other blood samples, the vital sign measurements will be performed before drawing blood samples in order to maximize the accuracy of blood sampling times while minimizing the potential effects of blood drawing on recordings obtained during safety assessments.

9.5.1.5.5 HEIGHT MEASUREMENTS

Height (cm) measurements will be obtained as designated in the Schedule of Procedures/Assessments (Table 2).

9.5.1.5.6 PHYSICAL EXAMINATIONS

Physical examinations will be performed as designated in the Schedule of Procedures/Assessments (Table 2). Documentation of the physical examination will be included in the source documentation at the site. Significant findings at the Screening Visit will be recorded on the Medical History and Current Medical Conditions CRF. Changes from screening physical examination findings that meet the definition of an AE will be recorded on the Adverse Events CRF.

9.5.1.5.7 ELECTROCARDIOGRAMS

Twelve-lead ECGs will be obtained as designated in the Schedule of Procedures/Assessments (Table 2).

An ECG abnormality may meet the criteria of an AE as described in this protocol (see Section 9.5.1.5.1) and the CRF Completion Guidelines. In these instances, the AE corresponding to the ECG abnormality will be recorded on the Adverse Events CRF.

For ECG abnormalities meeting criteria of an SAE (see Section 9.5.1.5.2), the site must fax or email the SAE report including the ECG report to the sponsor using the SAE form (see Section 9.5.4.1).

9.5.1.5.8 ECHOCARDIOGRAM

Echocardiograms will be obtained on the Schedule of Procedures/Assessments (Table 2). Valvular regurgitation in echocardiogram will be rated absent, trace, mild, moderate, or severe for the aortic, mitral, and tricuspid valves; the rating will be absent or present for the pulmonic valve. The evaluations will be based on guidelines from the American Society of Echocardiography. Pulmonary artery pressure will be estimated from the tricuspid regurgitant jet velocity.

9.5.1.5.9 OTHER SAFETY ASSESSMENTS

WRAML-2

The WRAML-2 administration will consist of the Core Battery, which provides scores on Verbal Memory, Visual Memory, and Attention/Concentration. There are 6 subtests (2 for each area). The tests provide standardized scores based on age and gender, and are appropriate for ages 5 to 90 years. The WRAML-2 will be used to assess lorcaserin effects on cognitive function. In addition, signs and symptoms of cognitive related AEs, including impairments in attention, memory, and adverse effects on schoolwork will be captured in the eCRF.

PHQ-9

The PHQ-9 is a multipurpose instrument for screening, diagnosing, monitoring and measuring the severity of depression:

- The PHQ-9 incorporates Diagnostic and Statistical Manual of Mental Disorders, 4th Edition (DSM-IV) depression diagnostic criteria with other leading major depressive symptoms into a brief self-report tool.
- The tool rates the frequency of the symptoms which factors into the scoring severity index.
- Question 9 on the PHQ-9 screens for the presence and duration of suicide ideation.
- A follow-up, non-scored question on the PHQ-9 assigns weight to the degree to which depressive problems have affected the patient's level of function.

C-SSRS

The C-SSRS collects information pertinent to suicidal ideation and actions. It consists of a Baseline version which will be administered at baseline and a Since Last Visit version which will be administered at the remaining visits. C-SSRS will be used to assess signal of depression and suicidal ideation or behavior. It will be performed at Baseline and at study visits as designated in the Schedule of Procedures/Assessments (Table 2).

Signs and symptoms of priapism (painful erection) and hyperprolactinemia (menstrual cycle abnormalities or galactorrhea) will be captured in the eCRF.

Hand X-Ray will be evaluated for any potential negative effect on bone age as designated in the Schedules/Assessments (Table 2). Neuromuscular sign assessment for serotonin syndrome will be performed as designated in the Schedule of Procedures/Assessments (Table 2) to screen for potential serotonergic syndrome components. Serotonergic syndromes that meet the diagnostic criteria will be captured by AE eCRF.

9.5.1.6 Other Assessments

9.5.1.6.1 PREGNANCY TEST

A urine pregnancy test in female subjects will be performed at designated time points as specified in the Schedule of Procedures/Assessments ([Table 2](#)).

9.5.1.6.2 URINE DRUG AND COTININE TEST

A 30-mL urine sample will be collected at designated time points as specified in the Schedule of Procedures/Assessments ([Table 2](#)). This sample will be tested for common drugs of use/abuse (eg, ethyl alcohol, cocaine, cannabinoids, phencyclidine, nicotine/cotinine, opioids [as a group], benzodiazepines, barbiturates, amphetamines).

9.5.2 Schedule of Procedures/Assessments

9.5.2.1 Schedule of Procedures/Assessments

[Table 2](#) presents the Schedule of Procedures/Assessments for the study.

Table 2 Schedule of Procedures/Assessments in Study APD356-A001-403

Phase:	Prerandomization ^a		Randomization										Other		
Period:	Screening		Treatment										Follow-Up		
Visit Number:	1	2 ^a	3	4	5	6	7	8	9	10	11 (EOT)	EOS	Un-scheduled	Early discontinuation	
Day:	-30 to -1	1													
Weeks ^{b,c} :		0	1	5	8	12	20	28	36	44	52	56			
Procedure															
Informed Consent	X														
Demography	X														
Medical History	X														
Prior/concomitant medication assessments	X	X	X	X	X	X	X	X	X	X	X		X	X	
Inclusion/exclusion criteria	X	X													
Physical Examination ^d	X	X	X			X		X			X	X	X	X	
Vital signs	X	X	X	X	X	X	X	X	X	X	X	X	X	X	
Height	X	X	X	X	X	X	X	X	X	X	X	X	X	X	
Weight	X	X	X	X	X	X	X	X	X	X	X	X	X	X	
Waist circumference	X	X		X		X		X	X		X	X	X	X	
Routine clinical laboratory tests	X	X	X	X		X		X			X	X	X	X	
Urinalysis	X		X	X		X		X	X		X	X	X	X	
Urine drug and cotinine test	X														
Fasting plasma glucose, Fasting Insulin, HOMA-IR, and HbA _{1c} sampling	X	X				X		X			X			X	
T4 and TSH	X							X			X			X	
AM serum cortisol		X									X				
Testosterone, Estradiol	X						X				X				

Table 2 Schedule of Procedures/Assessments in Study APD356-A001-403

Phase:	Prerandomization ^a		Randomization									Other		
Period:	Screening		Treatment									Follow-Up		
Visit Number:	1	2 ^a	3	4	5	6	7	8	9	10	11 (EOT)	EOS	Un-scheduled	Early discontinuation
Day:	-30 to -1	1												
Weeks ^{b,c} :		0	1	5	8	12	20	28	36	44	52	56		
Procedure														
Pregnancy test (Urine)	X	X	X	X	X	X	X	X	X	X	X	X		
Randomization		X												
IxRS	X	X		X	X	X	X	X	X	X	X			
Study drug dispensing		X		X	X	X	X	X	X	X			X	
Collect study medication				X	X	X	X	X	X	X	X	X	X	X
Drug accounting and compliance			X	X	X	X	X	X	X	X	X		X	X
AE monitoring	X	X	X	X	X	X	X	X	X	X	X	X	X	X
ECG		X						X			X	X		X
Echocardiograph	X ^f							X			X			X
CDC growth chart	X	X		X		X		X	X		X	X	X	X
Tanner Staging	X	X						X			X	X	X	X
C-SSRS		X	X	X	X	X	X	X	X	X	X	X	X	X
WRAML-2		X		X				X			X	X		X
PHQ-9		X	X	X		X	X		X		X	X		X
Hand x-ray for bone age		X				X		X			X			X
OC, PICP, and Hydroxy-proline		X						X			X			X
Urine NTX		X						X			X			
PK/PD blood sampling						X		X	X		X			X

Table 2 Schedule of Procedures/Assessments in Study APD356-A001-403

Phase:	Prerandomization ^a		Randomization										Other		
Period:	Screening		Treatment										Follow-Up		
Visit Number:	1	2 ^a	3	4	5	6	7	8	9	10	11 (EOT)	EOS	Un- scheduled	Early discon- tinuation	
Day:	-30 to -1	1													
Weeks ^{b,c} :		0	1	5	8	12	20	28	36	44	52	56			
Procedure															
Prolactin	X							X			X			X	
Standardized age-appropriate lifestyle modification counseling ^e		X	X	X	X	X	X	X	X	X			X		

AE = adverse event, AM = morning; CDC = Centers for Disease Control and Prevention, C-SSRS = Columbia-Suicide Severity Rating Scale, ECG = electrocardiogram, EOS = End of Study, EOT = End of Treatment, HbA_{1c} = hemoglobin A1c, HOMA-IR = Homeostatic Model Assessment of Insulin Resistance, IxRS = interactive voice or web response system, NTX = N-telopeptide, OC = osteocalcin; PHQ-9 = The Patient Health Questionnaire, PICP = carboxyterminal propeptide of type I procollagen, PK = pharmacokinetics, T4 = thyroxine, TSH = thyroid stimulating hormone, WRAML-2 = Wide Range Assessment of Memory and Learning-2.

^a: Baseline measurements will be collected on Day 1, before drug administration unless specified otherwise.

^b: Window ± 7 days for all visits after Visit 2 except for Weeks 12 and 28 (the window for these visits will be broader at ± 14 days). Week is shown unless otherwise indicated.

^c: On the day of the Week 12, 28, and 52 clinic visits, subjects will take their morning dose of study drug on the day before their scheduled clinic visit. On the day of the clinic visit, subjects will be instructed to take their study drug at approximately the same time as the morning before, with no additional doses taken that day. Two blood samples for determination of plasma concentrations of lorcaserin will be taken: predose (within 30 minutes before dosing) and within 1 to 3 hours after dosing. On the day of the Week 36 clinic visit, subjects will take the morning dose at home, and 1 blood sample for determination of plasma concentrations of lorcaserin will be collected at the investigational site within 4 to 6 hours after dosing. Dose times **must** be recorded for the last 2 dosing times prior to the clinic visit.

^d: Includes a neuromuscular assessment

^e: Lifestyle modification counseling will also be performed at Weeks 3, 24, 32, 40, and 48 in addition to counseling at the scheduled visits in [Table 2](#).

^f: Echocardiographic assessments will be performed during screening period after subjects have met all other inclusion and exclusion criteria.

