9 INVESTIGATIONAL PLAN

9.1 Overall Study Design and Plan

This is a multicenter, randomized, double-blind, placebo-controlled, parallel-group study in obese adolescents ages 12 to 17 years. Approximately 360 subjects will be randomized in a 1:1 ratio to Belviq XR 20 mg QD (180 subjects) and placebo (180 subjects). Subjects will be stratified by sex. Subjects will receive Belviq XR 20 mg or placebo QD in a 1:1 ratio for up to 52 weeks. Throughout the duration of the study, subjects will be encouraged to adhere to a lifestyle modification program that includes a standardized, age-appropriate diet and exercise counseling (see [Appendix 2](#)).

The study will consist of 2 phases: Prerandomization and Randomization. The Prerandomization Phase will last up to 30 days and consists of 1 visit during which subjects will be screened for eligibility. The Randomization Phase consists of a Treatment Period and a Follow-Up Period. The Treatment Period will last for a maximum of 52 weeks, with visits at Weeks 1, 5, 8, 12, 20, 28, 36, 44, and 52; the Follow-Up Period will extend from the End of Treatment (EOT) visit to the End of Study (EOS) visit.

Subjects who screen fail can be re-screened only once after 60 days. All subjects will continue in the study until the 52-week evaluation is completed. Subjects who discontinue treatment prematurely will be followed up until study completion.

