(NOTE: All female subjects will be considered to be of childbearing potential unless they have been sterilized surgically [ie, bilateral tubal ligation, total hysterectomy, or bilateral oophorectomy, all with surgery at least 1 month before dosing]).

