9.5.4.2 Reporting of Pregnancy and Exposure to Study Drug through Breastfeeding

Any pregnancy in which the estimated date of conception is either before the last visit or within 28 days of last study treatment or any exposure to study drug through breastfeeding during study treatment or within 28 days of last study treatment must be reported.

If an adverse outcome of a pregnancy is suspected to be related to study drug exposure, this should be reported regardless of the length of time that has passed since the exposure to study treatment.

A congenital anomaly, death during perinatal period, an induced abortion, or a spontaneous abortion are considered to be an SAE and should be reported in the same time frame and in the same format as all other SAEs (see [Section 9.5.4.1](#)).

Pregnancies or exposure to study drug through breastfeeding must be reported by fax or email as soon as possible but no later than 1 business day from the date the investigator becomes aware of the pregnancy. The contact information for the reporting of pregnancies and exposure to study drug through breastfeeding is provided in the Investigator Study File. The Pregnancy Report Form must be used for reporting. All pregnancies must be followed to outcome. The outcome of the pregnancy must be reported as soon as possible but no later than 1 business day from the date the investigator becomes aware of the outcome.

A subject who becomes pregnant must be withdrawn from the study.

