9.5.5 Completion/Discontinuation of Subjects

The investigator may withdraw the subject from the study at any time for safety or administrative reasons. A subject may elect to discontinue the study at any time for any reason. All subjects will continue in the study until the 52-week evaluation is completed. Subjects who discontinue treatment prematurely will be followed up until study completion. All subjects who discontinue the study are to complete the study's early discontinuation procedures indicated in the Schedule of Procedures/Assessments ([Table 2](#)).

The investigator will promptly explain to the subject involved that the study will be discontinued for that subject and provide appropriate medical treatment and other necessary measures for the subject. A subject who has ceased to return for visits will be followed up by mail, phone, or other means to gather information such as the reason for failure to return, the status of treatment compliance, the presence or absence of AEs, and clinical courses of signs and symptoms.

Subjects who discontinue early from the study will be discontinued for 1 of these primary reasons: AE(s), lost to follow-up, subject choice, withdrawal of consent, pregnancy, study terminated by sponsor, or other. In addition to the primary reason, the subject may indicate 1 or more of secondary reasons for discontinuation. Study disposition information will be collected on the Subject Disposition CRF.

Detailed retention strategies will be developed and included in study manual. These include a highly trained and competent staff, easy access to the clinic, reminder and follow-up calls, interactive group sessions with games and hands-on nutrition and physical activity demonstrations, random raffle drawings, social events, birthday and holiday cards, and newsletters. In addition, home visits for assessments of families will be an option, as needed, to maximize data collection. This detailed retention plan will help prevent missing data.

A subject removed from the study for any reason may not be replaced.

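### Table 2 marks no urine pregnancy test at the Early discontinuation visit, and no section clearly requires a later one for girls who leave the study, although conceptions up to 28 days after the last dose are reportable

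*Protocol*

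**What the plan says.** Section and table numbers refer to the latest protocol version in the document, the one limited to ages 12 to 17 with echocardiography in Table 2.

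- **Timing of the test.** Section 9.5.1.6.1 leaves timing to Table 2: "A urine pregnancy test in female subjects will be performed at designated time points as specified in the Schedule of Procedures/Assessments". In Table 2 the row beginning "Pregnancy test (Urine" is marked at Visits 1 to 11 (Screening to Week 52) and at End of Study (EOS, Week 56). The Unscheduled and Early discontinuation cells are blank, and no footnote adds a test.
- **Who is tested.** The note to the exclusion criteria in Section 9.3.2 reads: "All female subjects will be considered to be of childbearing potential unless they have been sterilized surgically".
- **Leaving the study.** Section 9.5.5: "All subjects who discontinue the study are to complete the study's early discontinuation procedures indicated in the Schedule of Procedures/Assessments".
- **Stopping treatment only.** The same section: "Subjects who discontinue treatment prematurely will be followed up until study completion". Section 9.1 adds that "the Follow-Up Period will extend from the End of Treatment (EOT) visit to the End of Study (EOS) visit".
- **Reporting duty.** Section 9.5.4.2 covers "Any pregnancy in which the estimated date of conception is either before the last visit or within 28 days of last study treatment" and requires every pregnancy to be followed to its outcome. The contraception criteria in Section 9.3.2 use the same 28 days.

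**The concern.** For a girl who completes the study, the schedule fits the reporting window: one test at the end of treatment and another four weeks later. For a girl who leaves the study, the exit visit carries no test and no later visit is clearly required of her. Section 9.5.4.2 draws no such distinction, so the reporting duty is the same for both.

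The blank looks like an oversight. Urinalysis is marked at Early discontinuation, so urine is already being taken. The hand x-ray and prolactin are also marked there, and at every other visit where either is marked the pregnancy test is marked too. Table 3 groups Early discontinuation with End of Treatment (EOT), and EOT has the test. Pregnancy is a listed reason for discontinuation in Section 9.5.5.

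What is at stake is ascertainment of pregnancies exposed to the drug. If detection is weaker among girls who leave, such pregnancies may be under-counted and not followed up. The efficacy analysis is untouched.

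**Working it through.** The plan states no figure on this point, so there is nothing to reproduce. The check is a reading of Table 2 plus simple arithmetic on visit times.

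**1. Is the blank real?** Table 2 has 14 columns: Visits 1 to 11, EOS, Unscheduled and Early discontinuation. Full rows such as vital signs carry 14 marks. The pregnancy row carries 12, which fill Visits 1 to 11 and EOS. The two empty cells are therefore Unscheduled and Early discontinuation, and a column shift in the PDF text does not explain them.

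**2. Who falls into the gap?**

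| Group | Governing text | Tests after the last dose |
|---|---|---|
| Completer | Table 2 | Week 52 (end of treatment) and Week 56 |
| Stops treatment, stays in study | 9.1 and 9.5.5 | All remaining visits to Week 52, and Week 56 |
| Leaves the study | 9.5.5 | None marked at exit; none clearly required later |

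Only the third group is affected. Within it, a girl who leaves at a scheduled visit may have been tested that day, and a girl lost to follow-up attends no exit visit.

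**3. How old can the last test be at exit?** Inputs: visit weeks from Table 2, and windows from footnote b (±7 days after Visit 2, ±14 days at Weeks 12 and 28).

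- Before Week 12, visits fall at Weeks 0, 1, 5, 8 and 12, so scheduled tests are nominally 1 to 4 weeks apart.
- From Week 12, visits fall at Weeks 12, 20, 28, 36, 44 and 52, so tests are 8 × 7 = 56 days apart.
- Widest gap with windows, for example Week 12 at −14 days to Week 20 at +7 days: 56 + 14 + 7 = 77 days, or 11 weeks.

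**4. How much reportable time follows the last scheduled test?** Assume the last dose is taken on the day of exit and no scheduled visit has been missed. Adding the 28-day window:

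- nominal maximum: 56 + 28 = 84 days
- maximum with windows: 77 + 28 = 105 days

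These are maxima. A girl who leaves soon after a scheduled visit has little more than the 28 days.

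**5. Does another section supply the test?**

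- Table 1 lists urine β-hCG under Other, and the routine laboratory row is marked at Early discontinuation. But Table 1 also lists HbA1c, T4/TSH, cortisol and prolactin, each of which has its own row and timing in Table 2. A Table 1 entry therefore does not place a test in the routine laboratory row. The separate pregnancy row and Section 9.5.1.6.1 point the same way.
- Table 3 groups Early discontinuation with Visit 11/EOT. That may suggest an EOS visit follows, but no section says so.
- Section 9.5.5 requires sites to contact subjects who stop attending. It gives no timing and does not name pregnancy among the things to ask about.

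**The case against.** The strongest reply has four parts.

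- **Section 9.5.4.2 is a reporting duty, not a testing duty.** Its clock starts when the investigator learns of the pregnancy. This stands: Table 2 does not contradict 9.5.4.2 in the strict sense. The schedule supports the duty less well in one group than in the others.
- **Girls who leave are not ignored.** AE monitoring and a physical examination are marked at Early discontinuation, SAEs are collected for 28 days after the last dose, and Section 9.5.5 requires contact with those who stop attending. This also stands. A reader might infer that pregnancies in girls who leave come to light only if the family volunteers them. The documents do not support that, because these are active inquiries. None of them is a test, however.
- **Tables 1 and 3 may already cover the gap.** Those readings cannot be excluded, but the text does not establish either. That ambiguity is itself a reason to reconcile the passages.
- **The longest gaps are worst cases.** They apply only from Week 12, the 11-week figure needs two windows at opposite extremes, and the documents do not say when dropout occurs. This stands, and the figures should be read as maxima.

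**Conclusion.** The point holds for girls who discontinue the study. Table 2 marks no pregnancy test at their exit visit and no section clearly requires a later one. From Week 12 their last scheduled test can be up to 8 weeks old at exit, or about 11 weeks with windows, provided no visit was missed. This is a small, inexpensive schedule correction that improves detection of exposed pregnancies.

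Two stronger readings should be resisted.

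- A reader might infer that every girl who stops early goes untested after her last dose. Sections 9.1 and 9.5.5 rule that out: those who stop only treatment stay in follow-up and keep the tests through Week 56.
- A reader might apply the 40% dropout in Section 9.7.2 (0.40 × 360 = 144), assume 40% to 60% are female, and conclude that 58 to 86 girls are affected. The documents do not support that count. The 40% is not split into treatment and study discontinuation or by sex. The count would also include girls tested on the day they leave and girls who attend no exit visit, whom a test there could not reach. The number affected is unknown.

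**What to change.** Reconcile Table 2 with Tables 1 and 3 and with Sections 9.5.4.2 and 9.5.5:

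- Mark the urine pregnancy test in the Early discontinuation column, using the urine already collected there for urinalysis.
- State in Section 9.5.5 whether subjects who leave the study also attend EOS. If they do not, state how the 28-day pregnancy window is covered through the contact that section already requires. A separate new call is not needed, since it would partly repeat existing SAE and contact duties.

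The cost is one table mark, a sentence of clarification, and one extra urine test for each girl who attends the visit. The mark does not help girls who never attend an exit visit; for them, cover depends on the Section 9.5.5 contact.
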